After verification of PD as assessed by BICR per RECIST 1.1 (modified to follow a maximum of 10 target lesions and a maximum of 5 target lesions per organ), subjects will have the option to remain on study and continue receiving the originally assigned trial treatment for a total of 35 cycles at the discretion of the investigator, provided they are deemed to be benefiting and are clinically stable (Section 7.1.2.7.6). Alternatively, subjects may choose to receive treatment with an appropriate second-line (2L) therapy as determined by the investigator.

At the discretion of the investigator and in consultation with the Sponsor, subjects assigned to the pembrolizumab arm who complete 35 treatment administrations may be eligible for retreatment with open-label pembrolizumab monotherapy at the time of radiographic disease progression (verified by BICR), provided that no other systemic therapy for SCLC has been administered. This retreatment is called the Second Course Phase (Section 6.2 and Section 7.1.5.5). Subjects in the saline placebo arm are not eligible for the Second Course Phase. Treatment assignment will be unblinded for those subjects who meet all criteria for

the Second Course Phase. Response or progression during the Second Course Phase will not be included in the analyses of the ORR or PFS endpoints in this trial.

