### **5.2.2 Timing of Dose Administration**

All trial treatments will be administered on an outpatient basis.

Trial treatment should be administered beginning on Day 1 of each cycle after all procedures and assessments have been completed (time points listed in Section 6). Day 1 of each cycle should occur as scheduled (or in a window of  $\pm 3$  days for administrative reasons only). Etoposide must be administered on 3 consecutive days without interruption (Days 1, 2, and 3) in Cycles 1 to 4.

For subjects who experience disease progression, investigators may elect to continue trial treatment until confirmation of disease progression or may elect to interrupt treatment by deferring the decision to continue/discontinue treatment in the trial until confirmation of disease progression per modified RECIST 1.1 at least 28 days from the date of imaging

demonstrating disease progression. Subjects for whom disease progression is not confirmed on subsequent imaging may resume treatment. Please see Section 5.8 for other exceptions.

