### **5.2.3 Trial Blinding**

This is a double-blinded trial with respect to pembrolizumab and placebo treatment. The subject, the investigator, and Sponsor personnel or delegate(s) who are involved in the treatment administration or clinical evaluation of the subjects will be unaware of the treatment assignments. The chemotherapy agents will be open-label. Pembrolizumab will be supplied to the sites in an open label manner. The study site's unblinded pharmacist will obtain each subject's study identification number and study drug assignment from the interactive voice response system/integrated web response system (IVRS/IWRS) and prepare the solutions for infusion. The unblinded pharmacist will provide the investigative staff with ready-to-use blinded pembrolizumab or saline placebo infusion solutions, packaged identically in order to maintain the blinding, for administration at scheduled infusion visits. In addition to emergency unblinding for severe or life-threatening AEs with potential immunologic etiology, non-emergency unblinding to pembrolizumab versus placebo administration may occur on an individual subject basis and only after consultation with the Sponsor at the time of (1) centrally verified disease progression and subject has discontinued all study treatments or, (2) when the subject has discontinued all study treatments and a new anti-cancer treatment is going to be started. Non-emergency unblinding, only after

consultation and approval from the Sponsor, is implemented through interactive response technology (IRT) by following the instructions in the IRT site user manual.

Additionally, imaging data will be centrally reviewed by radiologists who are blinded to subject treatment assignment, and the allocation schedule will be blinded in the database, preventing aggregate analysis.

See Section 7.1.4.2, Blinding/Unblinding, for a description of the method of unblinding a subject during the trial, should such action be warranted.

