Note: The number of treatments is calculated starting with the first dose. Subjects who stop trial treatment after receiving 35 doses of pembrolizumab or saline placebo may be eligible for the Second Course Phase (retreatment) if they progress after stopping trial treatment, provided they meet the requirements detailed in Section 7.1.5.5. Only subjects who were assigned to the pembrolizumab arm may be retreated in the Second Course Phase for up to an additional 17 cycles (approximately 1 year).

For subjects who are discontinued from trial treatment but continue to be monitored in the trial, all visits and procedures, as outlined in the trial flowchart, should be completed.

Discontinuation from trial treatment is "permanent." Once a subject is discontinued, he/she shall not be allowed to restart treatment.

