- Absence of progressive tumor at critical anatomical sites (eg, cord compression) requiring urgent alternative medical intervention (including immediate need for surgery or WBRT in the case of new brain metastases).

Any subject deemed **clinically unstable** should be discontinued from trial treatment at BICR verification of site-assessed first radiologic evidence of PD and is not required to have repeat imaging for PD confirmation.

In determining whether or not the tumor burden has increased or decreased per irRECIST, the local site investigator should consider all target and non-target lesions as well as any incremental new lesion(s).

Disease progression will be considered to be “not confirmed” at repeat imaging if ALL of the following occur (as assessed by irRECIST):

- Target lesion sum of diameters is <20% or <5 mm absolute increase compared to nadir
- Non-target disease resulting in initial PD is stable or qualitatively improved
- New lesion resulting in initial PD is stable or qualitatively improved
- No incremental new lesion(s) since last evaluation
- No incremental new non-target lesion progression since last evaluation

If repeat imaging does not confirm PD per irRECIST as assessed by the local site investigator and the subject continues to be clinically stable, treatment may continue and follow the regular imaging schedule.

Disease progression will be considered to be “confirmed” at repeat imaging if ANY of the following occur (as assessed by irRECIST):

- Target lesion sum of diameters reaches or remains  $\geq 20\%$  and  $\geq 5$  mm absolute increase compared to nadir
- Non-target disease shows unequivocal progression, or the non-target disease resulting in initial PD is qualitatively worse
- New lesions appear for the first time, or the new lesions resulting in initial PD are increased in size or number

If repeat imaging confirms PD due to any of the scenarios listed above, subjects will be discontinued from study therapy.

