Repeat tumor imaging shows SD, PR or CR by irRECIST at the local site	Continue regularly scheduled imaging assessments	Continue study treatment at the local site investigator's discretion	Continue regularly scheduled imaging assessments	May restart study treatment if condition has improved and/or clinically stable per investigator's discretion. Next tumor imaging should occur according to the regular imaging schedule outlined in the protocol

Abbreviations: BICR=blinded independent central review; CR=complete response; irRECIST=immune-related Response Evaluation Criteria in Solid Tumors; N/A=not applicable; PD=progressive disease; PR=partial response; SD=stable disease

Abbreviations: BICR=blinded independent central review, irRECIST=immune-related Response Evaluation Criteria in Solid Tumors, PD=progressive disease, PI=principal investigator, RECIST=Response Evaluation Criteria in Solid Tumors

\*If subject is clinically stable, may continue study treatment at the local site investigator’s discretion while awaiting verification of PD per RECIST 1.1 by BICR and/or confirmatory tumor imaging by site by irRECIST.

Figure 2 Imaging and Treatment for Clinically Stable Subjects After First Radiologic Evidence of PD Assessed by the Site

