#### **7.1.5.6 Continued Treatment Following Verified Progressive Disease**

Subjects who are deemed by the investigator to be benefiting clinically despite documented PD assessed by BICR using RECIST 1.1 (modified to follow a maximum of 10 target lesions and a maximum of 5 target lesions per organ), may remain on study and continue receiving the originally assigned trial treatment for a total of 35 cycles. Continued post-PD treatment is optional and will be determined at the discretion of the investigator (in consultation with the Sponsor).

Subjects who meet the following criteria will be eligible for continued post-PD treatment:

- Documentation of PD will be defined as BICR assessment.
- AEs (except alopecia and peripheral neuropathy) due to therapy must have improved to NCI CTCAE 4.0 Grade  $\leq$ 1.
- If a subject is unstable as a result of a new or progressing brain metastasis(es), the subject will not be eligible for continued treatment.
- ECOG Performance Status of 0 or 1.
- Subject must not have received any non-study systemic anti-cancer therapies.
- Subject has adequate organ function as indicated by the laboratory assessments listed in Section 5.1.2.

Visit requirements are outlined in the Trial Flow Chart (Section 6.1). Survival assessments and their respective entries into the database may be required more frequently around the time of the projected analyses (eg, DMC reviews, interim analyses). Specific procedure-related details are provided above in Section 7.1.

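### Table 8 lets a subject discontinued as clinically unstable at verified progression restart study drug; Section 5.8.1 forbids this, and Table 8 does not require clinical stability

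*Combined protocol and SAP*

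**What the plan says.** The rules for a subject who is clinically unstable at first progression are spread over four places.

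- **Section 7.1.2.7.6, text.** The subject "should be discontinued from trial treatment at BICR verification of site-assessed first radiologic evidence of PD". Repeat imaging is not required. The same section defines clinical stability: neurological stability without steroids, no symptoms or signs of clinically significant progression, no decline in ECOG status, no rapid progression, and no progressing tumor at a critical site.
- **Table 8, unstable column.** The first row says to discontinue treatment and leaves a confirmatory scan to the physician. The last row covers a repeat scan showing SD, PR or CR by irRECIST at the site: "May restart study treatment if condition has improved and/or clinically stable", per investigator's discretion.
- **Section 5.8.1.** Discontinuation from trial treatment is called permanent: "Once a subject is discontinued, he/she shall not be allowed to restart treatment". The only later treatment that this section describes is the Second Course Phase, for subjects who stop after 35 doses.
- **Section 2.1.** After BICR-verified progression, subjects may stay on the assigned treatment "provided they are deemed to be benefiting and are clinically stable (Section 7.1.2.7.6").

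**The concern.** One subject receives two incompatible instructions. If Section 5.8.1 governs, the restart cell in Table 8 can never be used. If Table 8 governs, the closing rule of Section 5.8.1 is untrue for this subject. A site can follow either in good faith, so the same clinical course can lead to renewed study drug at one site and permanent discontinuation at another.

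The second problem is the threshold for restart. The and/or makes improvement sufficient without stability. The subject concerned has verified progression and was too unwell to stay on treatment, so the test for giving drug again should not be looser than the test for a subject who never became unstable. At stake are who may receive study drug after verified progression, and consistency between sites.

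**Working it through.** No arithmetic applies. The check is to follow one subject through the text.

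1. **Entry.** BICR verifies first progression and the subject is clinically unstable. The text of Section 7.1.2.7.6 and the first row of Table 8 agree that trial treatment is discontinued.
2. **Repeat scan.** The physician opts for a scan at 4 weeks or more, and the site reads it as SD, PR or CR by irRECIST. The last row of Table 8 allows restart. Section 5.8.1 bars it. The Second Course does not apply, because the subject did not stop after 35 doses.
3. **Can the first step be read as a hold?** The protocol has a separate term for a hold. Section 5.2.2 says that investigators "may elect to interrupt treatment by deferring the decision to continue/discontinue treatment in the trial" until progression is confirmed. Table 8 and Section 7.1.2.7.6 instead use the language of discontinuation, which is also the language of Section 5.8.1.
4. **Does Section 5.8.1 exempt this case?** Its list of mandatory reasons includes confirmed radiographic progression, and here progression was not confirmed. But the no-restart sentence is not limited to that list. It applies to any subject once discontinued and does not mention Table 8.
5. **What does the and/or require?** The subject was unstable at the outset, so reaching stability is itself an improvement. The stability limb therefore adds nothing, and the working test is improvement alone. Section 2.1 asks for benefit and stability together.
6. **Does it reach the analyses?** Section 8.6.1.1 dates the primary PFS event at the first BICR-documented progression, whether or not study drug has stopped. In Table 11, the second PFS sensitivity analysis turns treatment discontinuation into an event only when there is no documented progression or death, so it does not apply here. OS runs from randomization to death in the ITT population. None of these depends on whether the subject restarts.

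**The case against.** The best defense rests on Section 5.2.2. It covers subjects with progression awaiting a confirmatory scan, is not limited to stable subjects, lets those whose progression is not confirmed resume, and points to Section 5.8 for other exceptions. On that view the Table 8 row is a specific exception to a general closing sentence, and the later word restart shows that a hold was meant all along. This has force as to intent: the authors probably did mean to allow a restart. It does not settle the text. Section 5.2.2 describes an elective interruption with the decision deferred, whereas Table 8 orders discontinuation. The section it points to is the one that bars restart.

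It is also fair to say that Section 2.1 governs continuing treatment, not restarting it. The conflict over stability is therefore by implication only.

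A reader might infer more than the documents support:

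- **A third, competing rule of stability plus Sponsor consultation.** No section states it. Section 2.1 requires benefit and stability without mentioning the Sponsor. Section 7.1.5.6 says continued treatment "will be determined at the discretion of the investigator (in consultation with the Sponsor"), but has no general stability test; it excludes only instability from brain metastases.
- **That the text of Section 7.1.2.7.6 requires stability of this subject.** The sentence "and the subject continues to be clinically stable, treatment may continue and follow the regular imaging schedule" describes subjects who were stable throughout.
- **That restarted doses escape safety follow-up.** Section 7.1.5.3.1 ties the visit to the last dose, and Sections 7.2 and 7.2.3.1 run AE and SAE reporting from cessation of treatment. A restart moves those dates.
- **That an unblinded subject could be restarted.** Non-emergency unblinding under Section 5.2.3, in the case of "centrally verified disease progression and subject has discontinued all study treatments", needs Sponsor consultation and approval. Section 7.1.4.2 takes a subject unblinded by the investigator off study drug.
- **A count of affected subjects.** Section 4.2.3.5 gives 7% pseudo-progression, but in melanoma, and the share of subjects unstable at first progression is not given. Unstable subjects are also probably less likely than others to have pseudo-progression, and their repeat scan is optional.

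**Conclusion.** The protocol is wrong as written on this point. The conflict between Table 8 and Section 5.8.1 is direct. The looseness of the and/or against Section 2.1 is a weaker point, by implication. The conclusion assumes that discontinuation means the same in Table 8 and Section 7.1.2.7.6 as in Section 5.8.1; the separate use of interruption in Section 5.2.2 supports this.

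Severity is minor. The case needs verified progression, clinical instability, an optional repeat scan, and a result of SD, PR or CR, so few subjects are likely to be affected. The documents do not allow a number. The effect is on the treatment of individual subjects and on consistency between sites. A reader might infer a threat to the primary endpoints; there is none for BICR-assessed PFS or for OS by ITT.

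**What to change.** State one rule. If restart is wanted:

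1. In Table 8 (first row, unstable column) and in the matching sentence of Section 7.1.2.7.6, replace discontinuation with: *interrupt treatment; discontinue permanently if PD is confirmed or the subject does not become clinically stable.*
2. In the restart cell, replace the condition with: *only if the subject has become clinically stable (Section 7.1.2.7.6).* The cell stays in the row for a repeat scan showing SD, PR or CR, so that scan is still needed.
3. In Section 5.8.1, after the no-restart sentence, add: *an interruption under Table 8 is not a discontinuation.*

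If restart is not wanted, set the restart cell to N/A and leave Section 5.8.1 as it stands.

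The cost is a few words in at most three places and a clarification letter to sites. Endpoints, analyses and sample size do not change.

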### 7.1.2.8 Tumor Tissue Collection: PD-L1 Status

Participation in this trial will be dependent upon supplying tumor tissue for PD-L1 testing from locations not radiated prior to biopsy. Subjects whose submitted tissue is not evaluable for PD-L1 status can still be eligible to participate in the study.

All subjects should submit either a newly obtained core or excisional biopsy or archival tissue (fine needle aspiration [FNA], endobronchial ultrasound [EBUS], guided transbronchial needle aspiration [TBNA], cell pellets, cytology, and blood smears are not adequate for both archival and new tissue samples) to a central laboratory for characterization of PD-L1 status prior to treatment allocation.

Note: Submission of formalin-fixed paraffin embedded tumor tissue sample blocks are preferred; if submitting unstained slides, the slides should be freshly cut and submitted to the testing laboratory within 14 days from the site slide section date, otherwise a new specimen will be requested.

If the sample is determined to be non-evaluable prior to testing by the central laboratory, a new sample should be submitted if available. This may include additional cut slides that are outside of the 14-day window noted above.

Individual subject PD-L1 status will not be disclosed to investigative sites and study subjects. Analyses by PD-L1 biomarker status will be limited and documented.

If the subject signs the Future Biomedical Research consent, any leftover samples that would be ordinarily discarded at the end of the main study will be retained for Future Biomedical Research.

### **7.1.3 Laboratory Procedures/Assessments**

Details regarding specific laboratory procedures/assessments to be performed in this trial are provided below. The total amount of blood/tissue to be drawn/collected over the course of the trial (from pre-trial to post-trial visits), including approximate blood/tissue volumes drawn/collected by visit and by sample type per subject can be found in the Laboratory Manual. Refer to the Trial Flow Chart (Section 6.0) for the timing of laboratory assessments.

#### **7.1.3.1 Clinical Laboratory Evaluations**

Clinical laboratory tests are specified in [Table 9](#).

Table 9 Clinical Laboratory Tests

Hematology	Hematocrit, hemoglobin, platelet count, WBC (total and differential), RBC, absolute lymphocyte count, absolute neutrophil count
Chemistry	Albumin, alkaline phosphatase, alanine aminotransferase, aspartate aminotransferase, bicarbonate (only required if done as part of standard of care by local laboratory), calcium, chloride, creatinine, glucose, phosphorus, potassium, sodium, total bilirubin, direct bilirubin (if total bilirubin >ULN), total protein, blood urea nitrogen or urea (one or the other should be collected per institutional standard; both of these laboratory tests are not required), LDH a
Thyroid Function Tests a	Total T3 or free T3 (T3 is preferred; if not available, free T3 may be tested), FT4, and TSH
Coagulation Parameters	PT/INR
Hepatitis Serologies b	HbsAg, HCV RNA (qualitative), Anti-HCV
Pregnancy test	If the urine test is not negative, then a serum test must be performed.
Urinalysis	Blood, glucose, protein, specific gravity Microscopic exam should be performed if abnormal results are noted

Abbreviations: FT4=free thyroxine; HbsAg=hepatitis B surface antigen; HCV=hepatitis C virus; LDH=Lactate dehydrogenase; PT=prothrombin time; RBC=red blood cells; T3=triiodothyronine; TSH=thyroid-stimulating hormone; ULN=upper limit of normal; WBC=white blood cells.
 
a If the local laboratory is unable to perform these tests, the site should submit the sample to the central laboratory for testing. Details are provided in the Laboratory Manual.
 
b Hepatitis C antibody testing is allowed in countries where HCV RNA is not part of standard of care. Testing for Hepatitis B and Hepatitis C should be performed as mandated by the local health authority.
	

For both the Initial Treatment Phase and the Second Course Phase:

- Screening laboratory tests should be performed within 10 days prior to the first dose of trial treatment, with the exception of the hepatitis serologies which may be performed within 28 days of the first dose of trial treatment in the Initial Treatment Phase only. Testing for hepatitis B and hepatitis C should be performed as mandated by the local health authority.
- Clinical laboratory tests must be conducted within 72 hours prior to first dose of trial treatment in each cycle, with the exception of laboratory tests performed by the central lab, which may be conducted up to 10 days prior to first dose of trial

treatment. Laboratory test results must be reviewed by the investigator or qualified designee and found to be acceptable prior to administration of first trial treatment.

- For laboratory tests performed by the central laboratory, any results not available prior to dosing must be reviewed by the investigator or qualified designee within 48 hours of receipt and found to be acceptable prior to subsequent administration of trial treatment.
- During the Initial Treatment Phase, laboratory tests will also be performed at the Day 8 Visit of each cycle. Results must be reviewed by the investigator or qualified designee within 48 hours of receipt.
- Unresolved abnormal laboratory test results that are drug-related AEs should be followed until resolution.

Laboratory tests do not need to be repeated after the end of treatment if laboratory test results are within the normal range.

